Attachment B: Participant Instructions for Measuring Blood Pressure

Checking your blood pressure at home is an important part of this study and helps you know when your blood pressure is high. Here is a quick guide on how to check your blood pressure at home.

1. Please take two blood pressure readings 1 minute apart in the morning and two readings 1 minute apart in the evening for every day for 2 weeks (for a total of 4 per day, and 64 readings over the 2 weeks).
2. Make sure the air plug of the blood pressure cuff is placed tight into the machine before taking your blood pressure.
3. Remove tight-fitting clothing from the left upper arm.
4. Sit in a chair with your feet flat on the floor. Put your left arm on a table or armrest so the cuff is about the same height as your heart. Sit for at least 5 minutes prior to taking your first blood pressure reading.
5. Place the blood pressure cuff on the left upper arm so that the white stripe is on the inside of the arm. Place the bottom of the blood pressure cuff about 1/2 inch above the elbow. Make sure that the air tube is pointed downward – it should run down the inside of your forearm and be in line with your middle finger (with the palm up). **See next page for a diagram.**
6. Make sure that you are comfortable, and your left arm is not tense. Keep your left hand open.
7. Press the Start/Stop button once with your other hand to take a measurement. You should feel the blood pressure cuff tighten when the blood pressure is being taken. Do not move or talk, and stay relaxed. Wait until the cuff deflates and your blood pressure is showing on the display. Once that has occurred, remove the blood pressure cuff.

You can use this table to keep track of whether or not you have measured your blood pressure at these times (Example: place 2X's under Day 1 AM after you've collected your two morning readings)

Week 1 (date range: / / to / /)							
	Day 1	Day 2	Day 3	Day 4	Day 5	Day 6	Day 7
AM							
PM							
Week 2 (date range: / / to / /)							
	Day 8	Day 9	Day 10	Day 11	Day 12	Day 13	Day 14
AM							
PM							
Week 3 (date range: / / to / /)							
	Day 8	Day 9	Day 10	Day 11	Day 12	Day 13	Day 14
AM							
PM							
Week 4 (date range: / / to / /)							
	Day 8	Day 9	Day 10	Day 11	Day 12	Day 13	Day 14
AM							
PM							

[figure not shown]
[figure not shown]
HOW TO APPLY CUFF

1

Put your arm through the cuff loop.

2

Insert your arm as indicated by the marker.

[figure not shown]
3

Position the arm correctly.

a) The air tube should run down the inside of your forearm and be in line with your middle finger.

[figure not shown]
b) The bottom of the cuff should be approximately $1/2''$ above your elbow.

c) Make sure that the blue stripe is on the inside of the arm and aligned with the middle finger (with the palm up).

4

Close the fabric (Velcro) fastener FIRMLY.

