Brief Summary	
In this research, we will conduct a double-blind, sham-controlled, randomized trial to examine the impact on cardiometabolic biomarkers of air pollution exposure reduction using home portable air cleaners (PACs) in a cohort of current adult patients at NYU Langone Health. This study is funded by CTSI (NIH/NCATS UL1TR001445) with two primary aims and two secondary/exploratory aims. In Aim 1, we will evaluate associations with PAC use with a priori specified biomarker of inflammation, tumor necrosis factor alpha (TNFα). We will determine if 4 weeks of home air filtration with PACs compared to sham is associated with significant reductions in TNFα concentrations when measured before and after intervention. Blood samples will be collected from 44 study participants before and after 4 weeks of PAC use (true and sham) for biomarker concentration measurement. In Aim 2, we will determine if reductions in fine particulate matter (<2.5 μm in diameter, PM_{2.5}) as a continuous variable are associated with significant reductions TNFα concentrations over a four-week period. In Exploratory Aim 1, we will explore associations between PAC use and concentrations of cardiometabolic biomarkers using a targeted proteomic panel, the Olink Explore 384 Cardiometabolic panel, measured before and after 4 weeks of intervention. This will be a hypothesis-generating analysis to identify possible novel biomarkers and pathways that may have importance in the physiological responses and clinical outcomes associated with air pollution exposure. In Exploratory Aim 2, we will explore if biomarkers identified in Exploratory Aim 1 with significant reductions after 4 weeks of PAC partially mediate the association between reductions in PM_{2.5} and changes in daily home blood pressure (BP) measurements. Participants will be given home BP monitors to transmit de-identified daily morning BP measurements to a secure database during the 4 week intervention period. Changes in morning systolic (BP) will be analyzed as the outcome of interest, with changes in biomarker concentrations evaluated as a mediator of the relations between pollution reduction and changes in BP.

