Objectives	
The primary objective of this research is to examine how PACs that reduce air pollution exposure affect cardiometabolic biomarkers and how those may mediate relationships with cardiovascular risk factors such as hypertension.
 
Specific Aim 1: To determine if 4 weeks of home air filtration with PACs compared to sham is associated with significant reductions in TNFα concentrations when measured before and after intervention.
 
Specific Aim 2: To determine if reductions in PM_{2.5} are associated with significant reductions TNFα concentrations over a four-week period.
 
Exploratory Aim 1: To identify novel biomarkers of the cardiometabolic effects of PM_{2.5} exposure with PAC use with a targeted proteomic panel, the Olink Explore 384 Cardiometabolic panel, measured before and after 4 weeks of intervention.
 
Exploratory Aim 2: To determine if novel biomarkers identified in Exploratory Aim 1 are mediators of the relationship between PAC use and home BP reductions after 4 weeks of PAC use.

Methodology	Randomized, double-blind, sham-controlled pilot study
Endpoint	
Aim 1 primary endpoint: Change in circulating concentration of TNFα
 
Aim 2 primary endpoint: Change in indoor PM_{2.5} concentration
 
Exploratory Aim 1 primary endpoint: Change in concentration of 384 circulating biomarkers associated with cardiometabolic risk
 
Exploratory Aim 2 primary endpoint: Change in average AM systolic blood pressure over study period

Study Duration	4 weeks
Participant Duration	Maximum: 4 weeks

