Exploratory Aim 2: To explore if changes in TNF α and other novel cardiometabolic biomarkers partially mediate the effects of PACs on home blood pressure. For this Aim, participants will monitor blood pressure daily during the 4-week intervention period using commercially available BP monitor with a paired data hub that transmits BP measurements to an online dashboard in real time. Participants will receive written and verbal instructions for proper BP recording technique at the baseline visit. They will record two measurements in a seated position each morning and evening during the study periods. The outcome of interest will be the mean of two AM systolic blood pressure measures. We will perform mediation analysis to analyze the direct and indirect effects of changes in significant biomarkers and PM_{2.5} changes on AM systolic BP. Based on our own pilot study of the effect of PAC use on AM systolic BP, we anticipate up to 30% missing BP measurements. We surveyed our prior pilot cohort regarding reasons for missing measurements and the predominant reported reason was forgetting; participants noted that they would have liked daily reminders. We will offer participants the option to receive daily text message reminders to record BP. These have been reported to be effective in other studies of home BP as well.

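### Attachment B tells participants to record blood pressure for 2 weeks and 64 readings, but the protocol needs 4 weeks (112 readings), so days 15-28 may be lost for Exploratory Aim 2

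*Combined protocol and SAP*

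**What the plan says.** Attachment B, item 1, asks for "two blood pressure readings 1 minute apart in the morning and two readings 1 minute apart in the evening", and sets the duration as "every day for 2 weeks (for a total of 4 per day, and 64 readings over the 2 weeks". Below the instructions is a log that participants may use to tick off readings. It has four blocks, Week 1 to Week 4, each with its own date range. The columns run Day 1 to Day 7 in Week 1 and Day 8 to Day 14 in Week 2, and then Day 8 to Day 14 again in both Week 3 and Week 4.

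The protocol gives a different duration. Under Exploratory Aim 2 in section 4.1, "participants will monitor blood pressure daily during the 4-week intervention period", and the daily schedule is the same four readings: "They will record two measurements in a seated position each morning and evening during the study periods". The Brief Summary has participants "transmit de-identified daily morning BP measurements to a secure database during the 4 week intervention period". The Objectives row of the Protocol Summary frames Exploratory Aim 2 as a search for "mediators of the relationship between PAC use and home BP reductions after 4 weeks of PAC use", and the Endpoint row gives its outcome as "Change in average AM systolic blood pressure over study period".

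A 2-week period also appears in the statistical text. The Statistical Analysis row of the Protocol Summary and section 10.3 both describe the PM2.5 average as taken over an intervention of 14 days.

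**The concern.** The handout and the protocol agree on how many readings to take each day but not on when to stop. The handout is what the participant has at home, and its only explicit duration is half of what the protocol requires. Its total is also inconsistent with its own duration, and no day after Day 14 is labelled anywhere on it. It could be read as 14, 16 or 28 days.

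At stake is the second half of the home BP series, which cannot be recovered once missed. Those days lie closest to the post-intervention blood draw, whose biomarker changes are the proposed mediators, and they bear most directly on an objective about BP after 4 weeks. If some participants stop at day 14 and others follow the log, the average over the study period is a 2-week average for some and a 4-week average for others.

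**Working it through.** Inputs:

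- Readings per day: 2 morning + 2 evening = 4 (Attachment B item 1 and section 4.1 agree).
- Duration in Attachment B item 1: 2 weeks = 14 days.
- Duration in section 4.1 and the Brief Summary: 4 weeks = 28 days.
- Total stated in Attachment B item 1: 64.
- Missing BP readings anticipated in section 4.1: up to 30%, an upper bound.

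**Reproducing the stated total** (readings = 4 × days):

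- 2 weeks: 4 × 14 = 56, not 64.
- 4 weeks: 4 × 28 = 112, not 64.
- Solving for days: 64 / 4 = 16. Neither document duration is 16 days.

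The stated 64 is therefore not reproduced under either duration.

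**Data from a participant who stops as item 1 directs:**

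- Readings: 56 of 112 = 50%.
- Mornings: 14 of 28 = 50%. Mornings are the natural unit, because section 4.1 defines the outcome as the mean of the two morning systolic readings.
- Days 15-28: none.

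**Data from a participant who stops on reaching 64 readings:** 64 / 112 = 57% of the planned readings, so 43% are lost.

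**Adding ordinary missingness.** Assume that the full 30% applies, that it falls on whole mornings, and that it is the same on whichever days are recorded:

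- 4-week recording: 0.7 × 28 = 19.6 usable mornings.
- 2-week recording: 0.7 × 14 = 9.8 usable mornings, or 9.8 / 28 = 35% of the planned mornings.

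With less than 30% missing, the counts lie between 9.8 and 14 mornings (2 weeks) and between 19.6 and 28 (4 weeks). The ratio stays at one half.

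The 112 is a nominal count for exactly 28 days. Section 7.6 allows the final blood draw up to 35 days after the air cleaner is switched on, so a participant who records until a late visit would exceed it.

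**The case against.** The other side has a good case on severity. Only an exploratory aim is involved, and section 10.3 calls those analyses hypothesis-generating. The log does show Week 3 and Week 4, each with date ranges and morning and evening boxes, so many participants would see that recording continues. Readings reach an online dashboard in real time (section 4.1), and section 8 provides weekly team meetings with biweekly participant reviews by coordinators, so someone who stopped could be noticed. Daily text reminders are offered. Two weeks of BP is also not worthless: section 2.1 cites a systolic effect over a median of 13.5 days.

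Most of this stands, and it makes the loss a risk and not a forecast. It does not remove the defect. Reminders are optional, the verbal instruction described in section 4.1 concerns technique and not duration, and nothing specifies a check or prompt at day 14.

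A reader might infer four stronger things that the documents do not support:

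- *That weeks 3-4 will be lost.* The four-week log and the dashboard make this uncertain.
- *That stopping at day 14 conflicts with the one-reading-per-day criterion in section 5.2.* That criterion concerns people who are unable to measure. Someone who stops because the sheet says so is not unable.
- *That the comparison between arms is biased.* No arm-specific version of the sheet is described, and participants are blinded. The supportable concern is lost data and unequal windows.
- *That 2 weeks was the intended duration, given the 14-day wording in the statistical text.* The Study Duration row, section 4.1 and section 6.1.4 all say 4 weeks.

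**Conclusion.** The inconsistency is certain: item 1 of Attachment B contradicts the protocol on duration, its total is wrong for either duration, and the log's day labels for Weeks 3 and 4 are wrong. The consequence is conditional. The loss of 14 of 28 mornings (56 of 112 readings), with none after day 14, is a per-participant worst case. It assumes that the participant follows item 1 over the log and is not prompted. How many would do so cannot be estimated from the documents. If some do and others do not, the Exploratory Aim 2 BP average covers unequal windows.

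The TNFα primary endpoint rests on two blood draws and does not depend on home BP readings. This is a should-fix: a limited consequence, but a plain error in participant-facing text that is nearly free to correct.

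**What to change.** 1. In Attachment B item 1, state 4 weeks, 4 readings per day, 112 readings in total.
2. In the log, relabel the Week 3 columns as Days 15-21 and the Week 4 columns as Days 22-28.
3. In the Statistical Analysis row of the Protocol Summary and in section 10.3, reconcile the 14-day description of the intervention with the 4-week period. Otherwise the same conflict remains in the PM2.5 variable that enters the mediation analysis alongside BP.
4. If any participants are still on study, tell them to continue recording past day 14. The documents do not show whether enrolment is open.

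The cost is negligible. Section 19 allows attachments to be changed without a protocol amendment, although section 13.2 sends participant materials to the IRB. Step 3 edits one phrase in two places in the protocol text and so needs an IRB-approved amendment. No change to visits, sample size or the primary analysis follows.

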Attachment C: Participant Instructions for Equipment Setup

Equipment Setup Instructions:

You have received:

1. Blood pressure cuff
2. Home Air Cleaner
3. Electricity monitor
4. Data Hub & cord
5. Air Pollution monitor & cord

- Plug the electricity monitor (4) into an outlet in your bedroom/sleeping area.
- Plug the Air Cleaner (2) into outlet number 1 on the electricity monitor.
- Turn the Air cleaner on to level 1. (You will leave it like this for the whole study.)
- Hang the air pollution monitor (5) to a wall on the opposite side of the same room – use the included command hook to secure it to a wall about 4 feet above an outlet.
- Plug in the air pollution monitor.
- Plug in the data hub (3) within 10 feet of where you will check your blood pressure (1). Please see separate instructions for use.

Bring to your final visit:

3. Electricity monitor
4. Data Hub & cord
5. Air Pollution monitor & cord
